6.5.2.4. Combined Solicited and Unsolicited Adverse Events

For clintrial.gov and EudraCT posting purposes, a summary of combined solicited (regardless of their duration) and unsolicited non-serious adverse events will be produced by System Organ Class and preferred terms and according to occurrence of each event. This analysis will be done on overall safety set.

Solicited symptom	Lower level code	Lower level term	
Pain	10022086	Injection site pain	
Fever	10016558	Fever	
Loss of appetite	10003028	Appetite lost	
Erythema	10022061	Injection site erythema	
Induration	10022075	Injection site induration	
Fatigue	10016256	Fatigue	
Headache	10019211	Headache	
Myalgia	10028411	Myalgia	
Arthralgia	10003239	Arthralgia	
Nausea	10028813	Nausea	
Chills	10008531	Chills	

Solicited adverse events will be coded by MedDRA as per the following codes:

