5.1.3.1.1. Solicited Safety Set (30 mins)

All subjects in the Exposed Set with any solicited adverse event data within 30 mins after vaccination.

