5.1.3.1.2. Solicited Safety Set (6 hours- Day 7)

All subjects in the Exposed Set with any solicited adverse event data 6 hours – Day 7 after vaccination.

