5.1.3.3. Overall Safety Set

All subjects who are in the Solicited Safety Set and/or Unsolicited Safety Set.

Subjects will be analyzed as "treated" (i.e., according to the vaccine a subject received, rather than the vaccine to which the subject may have been randomized).

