6.5. Analysis of safety

6.5.1. Analysis of safety planned in the protocol

Safety analysis will be performed on the solicited safety set for solicited reactions and on unsolicited safety set for unsolicited adverse events.

Analysis of Solicited Local, Systemic and Other Adverse Events

All solicited adverse events will be summarized according to defined severity grading scales.

205343 (MENACWY CONJ-032 [V59_71]) Statistical Analysis Plan Amendment 1 Final

Frequencies and percentages of subjects experiencing each adverse event will be presented for each symptom severity. Summary tables showing the occurrence of any local or systemic adverse event overall and at each time point will also be presented.

Post-vaccination solicited adverse events reported from Day 1 to Day 7 will be summarized for the intervals Day 1 (6 hours) – Day 3, Days 4-7, Day 1 (6 hours) – Day 7 by maximal severity and by study group. Separate analyses will be performed for solicited AEs reported 30 minutes after vaccination. The severity of solicited local adverse events, including injection-site erythema and induration, will be categorized based on linear measurement: Absent < 25 mm, Mild (25-50 mm), Moderate (51-100 mm), Severe (> 100 mm).

Injection site pain and systemic reactions, including fatigue, headache, myalgia, arthralgia, chills, nausea, loss of appetite, occurring up to 7 days after each vaccination will be summarized according to "mild", "moderate" or "severe". The assessment of the intensity of solicited AEs is detailed in section 8.3.3.2.1 of the protocol.

Each solicited local and systemic adverse event will also be further summarized as "absent" versus "any".

Use of antipyretics and analgesics will be summarized by frequency, by type of use (prophylactic versus treatment) and percentage of subjects reporting use.

Body temperature will be summarized separately according to the 2 schemes described below and will be broken down according to route of measurements (axilla, oral cavity, rectum, tympanic membrane):

- by 1°C increments: <36.0, 36.0-36.9, 37.0-37.9, 38.0-38.9, 39.0-39.9, ≥40°C;
- According to different cut-offs (< versus ≥): 38.0, 38.5, 39.0, 39.5, 40.0°C.

Solicited AEs reported within 30 minutes post-vaccination will be summarized in a separate table.

Analysis of Unsolicited Adverse Events

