6.5.2. Additional considerations

Summaries of safety will be presented using frequencies and percentages within each study group. No statistical comparisons among the study groups with respect to any of the safety parameters will be performed.

Incomplete/partial data in the e-Diary (e.g. local and/or systemic reactions reported only for some days and/or for some reactions) will not be considered as protocol deviations. Summary statistics for local and systemic adverse events will not include missing data, hence numerators and denominators may change from day to day and for the different reactions.

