6.5.2.2. Solicited Adverse Events

For details please refer to Section 8.1.3 of the protocol.

Fever, defined as a body temperature of \geq 38°Cirrespective of route of measurement, will be integrated to the summaries as a systemic adverse event.

The analyses will encompass summaries of the data on five levels:

- 1. Daily reports of subjects with solicited adverse events.
- 2. Time of first onset of solicited adverse events (excluding 30 min measurement).
- 3. Solicited adverse events, maximum event severity by event and interval [6h day 3, day 4 -7, and 6h day 7, each without 30 min].
- 4. Duration of solicited adverse events, including ongoing AE after Day 7.
- 5. Solicited adverse events and indicators of solicited adverse events (use of antipyretics and analgesics for treatment or prophylaxis), occurrence of at least one event by category (local, systemic) and interval 6h-Day 3, Day 4-7 and 6h-Day 7, each without 30 min.

For each of the time points or time intervals presented in the summaries, only subjects with at least one plausible observation (i.e., any non-missing values but excluding "Not done/unknown" and implausible values) for the solicited adverse events in the interval of interest will be considered. Subjects without any plausible data (i.e. missing values or reported as "Not done/unknown" and implausible values) will be removed from the denominator to prevent a downward bias (towards zero).

Level 1: Daily reports of solicited adverse event

For each of the time points (6h, days 2, 3, 4, 5, 6 and 7) only subjects with at least one plausible observation (i.e., any non-missing values but excluding "Not done/unknown" and implausible values) for the solicited adverse event in the interval of interest will be considered. Subjects without plausible data (i.e. missing values or reported as "Not done/unknown" and implausible values) will be removed from the denominator in order to prevent a downward bias (towards zero). Data collected will be summarized (frequencies and percentages of subjects) by study group, solicited adverse event and time point.

Level 2: Time of first onset of solicited adverse events

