12. ANNEX 2: SUMMARY ON ELIMINATION CODES

Table 5Safety Sets

PD code	PD Description	Study Period	All Exposed Set	Overall Safety Set	Safety Set, Unsolicited AEs	Safety Set, Solicited AEs
	Exclusion code		EXPFL	SAFFL	SSUFL	SSSFL
1030	Study vaccine not administered AT ALL	Day 1 – Day 181	EXC	EXC	EXC	EXC
2150	Subject did not provide any post-vaccination unsolicited safety data	Day 1 – Day 181	None	None	EXC	None
2160	Subject did not provide any post-vaccination solicited safety data	Day 1- Day 7	None	None	None	EXC

EXC = excluded from this analysis set.

Table 6 Immunogenicity Sets

PD code	PD Description	Study Period	FAS Day 29	PP Day 29
	Exclusion code		FAS29FL	PPS29FL
1030	Study vaccine not administered AT ALL	All Study	EXC	EXC
2100.1	Serological results are not available at Day 1 for any of the serogroups	Day 1	EXC (for 4-fold rise only)	EXC (for 4-fold rise only)
2100.2	Serological results are not available at Day 29 for any of the serogroups	Day 29	EXC	EXC
2120.1	Obvious deviation from Laboratory Manual or error in laboratory data at Day 1 for any of the serogroups	Day 1	None	EXC (for 4-fold rise only)
2120.2	Obvious deviation from Laboratory Manual or error in laboratory data at Day 29	Day 29	None	EXC
1050	Randomization failure	Day 1 – Day 29	None	EXC
1070	Vaccination not according to protocol	Day 1	None	EXC
1040	Administration of forbidden vaccine	Day 1 – Day 29	None	EXC
2010	Subject did not meet entry criteria	Day 1 – Day 29	None	EXC
2040	Administration of forbidden medication	Day 1 – Day 29	None	EXC
2090.1	Day 1 blood draw performed out of planned visit window	Day 1	None	EXC (for 4-fold rise only)
2090.2	Day 29 blood draw performed out of planned visit window	Day 29	None	EXC

FAS = Full Analysis Set; PPS=Per Protocol Set; M=Month EXC = excluded from this analysis set.

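### The combined registry table (SAP 6.5.2.4) puts the 11 solicited terms on a set that keeps subjects without diary data, and states no denominator for those terms

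*SAP*

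**What the plan says.** The references are to SAP Amendment 1.

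- **Combined table (6.5.2.4).** Solicited and unsolicited non-serious events are tabulated by system organ class and preferred term for registry posting. Eleven solicited reactions are given MedDRA codes for this purpose. On the population, the section says only "This analysis will be done on overall safety set".
- **Overall Safety Set (5.1.3.3).** "All subjects who are in the Solicited Safety Set and/or Unsolicited Safety Set". Solicited data are therefore not required for membership.
- **Two solicited sets (5.1.3.1).** One is "All subjects in the Exposed Set with any solicited adverse event data within 30 mins after vaccination"; the other is "All subjects in the Exposed Set with any solicited adverse event data 6 hours – Day 7 after vaccination".
- **Elimination codes (Annex 2, Table 5).** Code 2160, "Subject did not provide any post-vaccination solicited safety data", excludes a subject from the solicited set but not from the Overall Safety Set.
- **Main safety analysis (6.5.1).** "Safety analysis will be performed on the solicited safety set for solicited reactions and on unsolicited safety set for unsolicited adverse events".
- **Denominator rule for the five levels of solicited summaries (6.5.2.2).** Subjects without plausible data "will be removed from the denominator to prevent a downward bias (towards zero".

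**The concern.** The SAP identifies a specific bias in 6.5.2.2 and guards against it there. In 6.5.2.4 it places the same reactions on a wider set and does not say whether the guard still applies. A programmer working from 6.5.2.4 alone would probably divide by the size of the named set. A subject who never completed a diary would then add to the denominator with no opportunity to report a reaction through the diary.

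This is the table that goes to the public registries. Readers there could see a lower percentage for a given reaction than the study report shows, with nothing to explain the difference. If diary completion differed between the groups, part of any between-group gap in the table would reflect completion and not the vaccines.

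**Working it through.** **Inputs.** The documents give no reaction rates and no expected share of subjects without diary data, so there is no figure of the plan's own to reproduce. I assume:

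- p, the rate of a reaction among subjects with diary data: 5%, 20% or 40%;
- m, the share of the Overall Safety Set with no diary data: 1%, 5% or 10%. The top value borrows the 10% dropout in Protocol 10.3, which is an allowance for evaluable subjects and not a diary figure;
- 486 subjects per group (Protocol 5.2.2.2.1), for scale only.

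**Step 1: who is in the set without a diary?** There are two kinds of subject. The first has unsolicited data but no solicited data (code 2160). The second has only the 30-minute on-site assessment, which goes into the eCRF and not the diary (SAP Section 2). The second kind belongs to the 30-minute solicited set, and so to the Overall Safety Set, without belonging to the 6 hours to Day 7 set.

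**Step 2: largest dilution.** If the set size is the base and subjects without a diary contribute no event of that term, the posted rate is p × (1 − m). The relative understatement is m and the absolute understatement is p × m.

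| m | Subjects of 486 | p = 5% | p = 20% | p = 40% |
|---|---|---|---|---|
| 1% | 4.9 | 4.95% | 19.8% | 39.6% |
| 5% | 24.3 | 4.75% | 19.0% | 38.0% |
| 10% | 48.6 | 4.50% | 18.0% | 36.0% |

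At p = 40% the loss is 0.4, 2.0 and 4.0 percentage points.

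**Step 3: allowance for other reporting routes.** If a fraction q of the subjects without a diary have the term recorded some other way, the posted rate is p(1 − m) + qm, and the understatement falls to m(p − q). For example, with p = 40%, m = 5% and an assumed q = 20%, the posted rate is 38.0% + 1.0% = 39.0%. Step 2 is therefore an upper bound.

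**Step 4: unequal completion.** With p = 40% in both groups and m = 5% against 1%, the posted rates are 38.0% and 39.6%, a gap of 1.6 points with no true difference. Nothing in the documents suggests that such an imbalance is expected.

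**The case against.** The strongest reply is that the SAP already deals with missing data. Section 6.5.2, the parent of 6.5.2.4, states: "Summary statistics for local and systemic adverse events will not include missing data, hence numerators and denominators may change from day to day". SAP 11.2 also removes subjects who withdraw or are lost to follow-up from the denominator for periods in which they have no safety data. On this view 6.5.2.4 simply does not repeat a general rule.

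That reply stands in part. It means the documents do not support the flat statement, which a reader might infer, that subjects without a diary are counted as reaction-free. Section 6.5.2.4 names a population and is silent on the denominator. The general rules do not clearly settle the matter, however. The 6.5.2 sentence follows a description of partly completed diaries and speaks of daily denominators. The 11.2 rule concerns withdrawal and loss to follow-up, and a subject with unsolicited data but no diary does have safety data for the period.

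Three further points against the concern are sound:

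- Subjects without a diary can still contribute these terms. Reactions first reported at a visit are entered as unsolicited events (Protocol 11.2). Solicited symptoms starting outside the window are also unsolicited (Protocol glossary). Reactions at 30 minutes are collected on site. For the same reason the combined table would not match the diary tables exactly under any denominator.
- The plan works to keep m small, through an eligibility criterion on diary compliance (Protocol 4.2) and daily alarms with alerts to sites (Protocol 5.6.14.1.1). Recipients are blinded (Protocol 5.3), which gives no reason to expect differential completion.
- Safety is descriptive, with no statistical comparison between groups (SAP 6.5.2).

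**Conclusion.** The point holds as a gap in specification with a small potential bias. Section 6.5.2.4 uses a set that keeps subjects without diary data, and does not carry over the rule in 6.5.2.2 that would remove them. If the set size is the base, the relative understatement is at most m: at an assumed 40% rate, between 0.4 points (m = 1%) and 4.0 points (m = 10%), less the events those subjects report verbally, at 30 minutes or on the adverse event form. Both p and m are assumptions.

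Two stronger readings are not supported. One is that the SAP removes such subjects in every other safety table; the rule is written for the solicited summaries of 6.5.2.2. The other is that a spurious vaccine difference will appear; that needs unequal diary completion, for which the documents give no evidence. The main solicited tables keep the stricter denominator, and the primary objective is unaffected.

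**What to change.** In SAP 6.5.2.4, state that for the 11 listed solicited terms both the numerator and the number at risk come from the Solicited Safety Set (6 hours to Day 7), and that all other terms use the Overall Safety Set. Where a subject without diary data has one of the 11 terms on the adverse event form or at 30 minutes, report those events in a footnote by group.

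Such subjects should not be added to the denominator only when they had the event. With D diary subjects and k added cases the rate becomes (pD + k)/(D + k), which exceeds p for any k above zero when p is below 1, so the bias is simply turned upwards.

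The cost is a short addition to the SAP and a term-specific denominator in one program. Annex 2 already lists a solicited-set flag; it must be the version for 6 hours to Day 7, not one met by the 30-minute assessment alone. The downside is that denominators differ by term within the table and a few events move to a footnote.

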6.5.2.5. Clinical Safety Laboratory Investigations

Not applicable

6.5.2.6. Concomitant Medication

Medications will be coded using the GlaxoSmithKline Drug Dictionary (GSKDRUG dictionary).

The frequencies and percentages of subjects starting/reporting concomitant medication within 29 days post-vaccination will be summarized overall and by study group.

7. ANALYSIS INTERPRETATION

7.1. Primary Immunogenicity Objective

The analysis population for the non-inferiority analysis is the Per Protocol Set (PPS).

To demonstrate non-inferiority of the investigational liquid MenACWY vaccines to the currently licensed MenACWY vaccine (*Menveo*), the lower limit of the two-sided 95% confidence interval (CI) for the hSBA GMT ratios for serogroup A at Day 29, must be greater than 0.5. Hypothesis testing will be performed at an overall significance level (α) of 2.5% (one-sided) using a non-inferiority margin of 0.5 for GMT ratios:

Null hypothesis (inferiority): $\mu_{ACWY_Liq30} - \mu_{ACWY} \le \log_{10}(0.5)$ versus

Alternative hypothesis (non-inferiority): $\mu_{ACWY_Liq30} - \mu_{ACWY} > \log_{10}(0.5)$

Where: 0.5 is the non-inferiority margin for the ratio of GMTs between Group

ACWY_Liq and Group ACWY; μ_{ACWY_Liq30} and μ_{ACWY} are the population means of the logarithmically (base of 10) transformed titers for serogroup A in Group ACWY_Liq and Group ACWY, respectively.

If the lower limit of the two-sided 95% CI for the hSBA GMT ratio is greater than 0.5, then we conclude non-inferiority.

7.2. Secondary Immunogenicity Objectives

Analysis of secondary objectives will be descriptive.

8. CONDUCT OF ANALYSES

Any deviation(s) or change(s) from the original statistical plan outlined in the protocol will be described and justified in the final study report.

8.1. Sequence of analyses

Only one analysis will be performed.

A CSR will be written and made available to the investigators.

Description	Analysis ID	Disclosure Purpose (CTRS=public posting, SR=study report, internal)	Dry run review needed (Y/N)	Study Headline Summary (SHS)requiring expedited communication to upper management (Yes/No)	Reference for TFL
Final analysis	E1_01	SR and CTRS	Y	Yes	All tables from the latest TFL TOC in eTMF

8.2. Statistical considerations for interim analyses

No interim analysis is planned.

9. CHANGES FROM PLANNED ANALYSES

Planned interim analyses will not be performed; eCRF and lab data will be analyzed at the same time since the sera results release will be occur later than initially planned.

This modification has no impact from the statistical analysis perspective and all considerations about result interpretations remain valid and unchanged.

10. LIST OF FINAL REPORT TABLES, LISTINGS AND FIGURES

The TFL TOC provides the list of tables/listings and figures needed for the study report. It also identifies the tables eligible for each analysis and their role (synopsis, in-text, post-text, SHS, CTRS, etc.).

The mock tables referred under column named 'layout' can be found in GSK SDD dedicated folder for standard tables.

The following group names will be used in the TFLs, to be in line with the T-domains:

Group order in tables	Group label in tables	Group definition for footnote
1	Menveo Liquid	Subjects who received MenACWY- Liquid
2	Menveo	Subjects who received Licensed MenACWY

11.2. Standard data derivation

Immunogenicity

- A seronegative subject is a subject whose titer is below the LOD.
- A seropositive subject is a subject whose titer is greater than or equal to the LOD.
- Values below the limit of detection will be set to half that limit.
- Four-fold rise is defined as:
 - For individuals whose pre-vaccination titers are < LOD, the post-vaccination titers must \geq max (4*LOD, LLOQ).
 - For individuals whose pre-vaccination titers are \geq LOD and \leq LLOQ, the post-vaccination titers \geq 4*LLOQ.
 - For individuals whose pre-vaccination titers are > LLOQ, post-vaccination ≥ 4*pre-vaccination titer.
- Handling of missing data: for a given subject and a given immunogenicity measurement, missing or non-evaluable measurements will not be replaced.

Reactogenicity and Safety

• Handling of missing data: Subjects will be analyzed to the extent that they are exposed to study vaccines and according to the available safety data for the subject during any study period. Subjects who withdraw early or who are lost to follow-up will be removed from the denominator for the time period in which they have no available safety data collected.

Duration in the Study

Duration in the study is defined in days as:

Last visit date $(visit x)^a$ – Enrollment date (visit 1) + 1

^aor premature discontinuation date (in case of withdrawal from the study)

The duration is missing if one of the dates is missing or incomplete.

Unsolicited Adverse Events

All adverse events will be characterized according to the date of occurrence related to the vaccination phase as follows:

- **Emergence before vaccination phase**: start date before the first date of injection of study vaccine.
- Emergence during vaccination phase: start date on or after the first date of injection of study vaccine or, adverse event increase in severity including to "serious" adverse event.

If start date is equal to the first date of injection then "timing" variable ("On injection day, before injection"/"On injection day, after injection") will be used to define whether the adverse event occurred before or after the injection.

If an adverse event start date is missing or unknown, the adverse event will be considered as emergent.

When start and/or end dates of an adverse event are only partially known, adverse events will be categorized as emergent before, during, or after vaccination phase using the following rules:

- If the partial end date is before (<) the study vaccination (i.e., year or year & month is/are before the study vaccination year or year & month) then the adverse event is emergent before vaccination phase.
- If the partial start date is equal or after (≥) the study vaccination (i.e., year or year & month is/are after or the same as the study injection year or year & month) then the adverse event is emergent during vaccination phase.

205343 (MENACWY CONJ-032 [V59_71]) Statistical Analysis Plan Amendment 1 Final

The maximum event severity is the greatest severity associated with a preferred term for a reported adverse event according to the following order: Mild < Moderate < Severe. Unknown/ Missing severity is considered as severe (except for the definition of emergence).

Multiple AEs with the same PT for the same subject are counted only once.

Vaccination-related Adverse Events are those for which the cause has been evaluated by the investigator, and recorded either as related or unknown/missing.

Prestudy, Concomitant and Post-Vaccination Medications

A **previous medication** is a medication used only before the first study vaccination (i.e. medication end date < first study vaccination date).

A **post-vaccination** medication is a medication used only after the second blood draw

All other medications are **concomitant**.

When start and/or end dates of a medication intake are missing, the medication is considered as concomitant with the study vaccination schedule.

If the study vaccination date is missing then the medication is considered as concomitant with the study vaccination schedule, provided that the study vaccine was administered to the subject.

The frequencies and percentages of subjects will be summarized overall and by study group.

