10.5. Derived and transformed data

- Immunogenicity
 - Assay cut-off and unit will be determined following validation of the MenACWY hSBAs. This will be documented in the clinical report.
 - A seronegative subject is a subject whose titer is below the LOD.
 - A seropositive subject is a subject whose titer is greater than or equal to the LOD.
 - The Geometric Mean Titers (GMTs) calculations are performed by taking the anti-log of the mean of the log concentration/titer transformations. Values to be used for the antibody concentrations/titers below the assay cut-off will be described in the Statistical Analysis Plan (SAP).
 - Handling of missing data: for a given subject and a given immunogenicity measurement, missing or non-evaluable measurements will not be replaced.
- Reactogenicity and Safety
 - Handling of missing data: Subjects will be analysed to the extent that they are exposed to study vaccines and according to the available safety data for the subject during any study period. Subjects who withdraw early or who are lost to follow-up will be removed from the denominator for the time period in which they have no available safety data collected.

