6.4. Immunogenicity

6.4.1. Analysis of immunogenicity planned in the protocol

The primary analysis will be based on the per-protocol set for analysis of immunogenicity. If, in any study group and timepoint, the percentage of vaccinated subjects with serological results excluded from the per-protocol set for analysis of immunogenicity is 5% or more, a second analysis based on the Full Analysis Set will be performed to complement the per-protocol analysis.

GMTs, Between-group ratios of GMTs and within-group Geometric Mean Ratios (GMRs)

The hSBA titers at each visit will be logarithmically transformed (base10) to obtain approximately normally distributed data. For each *N. meningitidis* serogroup A, C, W and Y, GMTs will be calculated, with their associated two-sided 95% CIs, by exponentiating the corresponding log-transformed means and their 95% CIs.

The between-group ratio of hSBA GMTs and corresponding 95% CI, at each of Day 1 and Day 29 against *N. meningitidis* serogroups A, C, W and Y will be obtained by exponentiating the between-group mean differences in log-transformed titers and the corresponding 95% CIs at each of the specified timepoints.

Within each study group and for each serogroup, GMRs will be calculated at Day 29 versus Day 1. The GMRs and 95% CIs will be constructed by exponentiating the withingroup mean differences in log-transformed titers and the corresponding 95% CIs.

The mean differences will be obtained from an Analysis of Covariance (ANCOVA) including pre-vaccination titer (Day 1) as a covariate and with vaccine group and center (if applicable) as factors in the model.

Percentages of subjects with $a \ge 4$ -fold rise in post-vaccination hSBA (Day 29)

The percentage of subjects with $a \ge 4$ -fold rise in post-vaccination hSBA (at Day 29 compared to Day 1) and associated two-sided 95% Clopper-Pearson CIs will be computed by group and *N. meningitidis* serogroups A, C, W and Y. Differences in percentages and associated 95% CIs between study groups will be calculated using the Miettinen and Nurminen score method. [Clopper, 1934; Miettinen, 1985]

Percentage of Subjects with hSBA titer ≥8 and ≥LLOQ* (Day 1 and Day 29)

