For each study group the percentage of subjects with hSBA titer ≥ 8 and \geq LLOQ* and associated two-sided 95% Clopper-Pearson CIs will be computed by the *N. meningitidis* serogroups A, C, W and Y on Day 1 and Day 29. Differences in percentages and associated 95% CIs between study groups will be calculated using the Miettinen and Nurminen score method. [Clopper, 1934; Miettinen, 1985]

*Note: To be assessed for each serogroup if the pre-defined LLOQ value for that serogroup is >8.

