6.4.2. Additional considerations

The ANCOVA is used to adjust for the potential baseline imbalance between study groups. The ANCOVA analysis will be performed for the primary endpoint.

In addition, an Analysis of Variance (ANOVA) model with vaccine group and center (if applicable) as factors will be fitted in order to compute the estimates (not adjusted for pre-vaccination titer) together with their associated 95% CIs by exponentiating the corresponding log-transformed means and their 95% CIs.

205343 (MENACWY CONJ-032 [V59_71]) Statistical Analysis Plan Amendment 1 Final

For the 'by country' subgroup analysis, the ANCOVA and ANOVA models will be fitted without country in the model.

Given the high likelihood of having centers with few subjects enrolled in the study; therefore, country will be used as a factor in the ANCOVA/ANOVA analyses instead of center.

Permutation test (sensitivity analysis on primary objectives)

Based on the covariate-adaptive vaccine assignment algorithm (see Section 14 (Annex 4)), the following permutation test [Wiens, 2006; Hasegawa, 2009 and Ernst, 2004] will be performed as a sensitivity analysis on the primary objective in the PPS.

For serogroup A, let $\mathbf{X} = (X_1, ..., X_N)$ the logarithmically-transformed hSBA titers for the ACWY_liq group and $\mathbf{Y} = (\mathbf{Y}_1, ..., \mathbf{Y}_N)$ the logarithmically-transformed hSBA titers for ACWY group at 1 month after vaccination. A non-inferiority permutation test can be obtained from a superiority permutation test on $\dot{\mathbf{X}} = (X_1 + \delta, ..., X_N + \delta)$ against $\dot{\mathbf{Y}} = (\mathbf{Y}_1, ..., \mathbf{Y}_N)$ with $\delta = 0.301 = -\log_{10}(0.5)$.

The original vaccine assignment algorithm Section 14 (Annex 4) will be used to rerandomize subjects belonging to the ACWY_Liq group and ACWY group (see step 2a) while keeping hSBA titers, covariates and entry order as observed. The procedure will be as follows:

- 1. Fit the ANCOVA model to obtain the test statistics T^* for the superiority of \dot{X} against \dot{Y} ;
- 2. Estimate the distribution of the corresponding test statistic with R=10 000 repetitions of the following two steps:
 - a. Re-randomize vaccine assignment of groups $\dot{\mathbf{X}}$ and $\dot{\mathbf{Y}}$ (original algorithm);
 - b. Re-fit the full ANCOVA model to re-obtain the test statistics T;

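### Does setting serogroup A titers below the LOD to half the LOD, with no sensitivity analysis on that value, undermine the non-inferiority conclusion?

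*SAP*

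**What the plan says.** Protocol 10.5 leaves the value for titers below the assay cut-off to the SAP. SAP 11.2 supplies it: "Values below the limit of detection will be set to half that limit". The opening note of SAP 6 applies the Annex 1 derivations to all analyses. The same annex defines detection: "A seropositive subject is a subject whose titer is greater than or equal to the LOD".

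SAP 6.4.1 gives the scale of analysis: "The hSBA titers at each visit will be logarithmically transformed (base10) to obtain approximately normally distributed data". SAP 7.1 states the hypotheses in terms of μ values that "are the population means of the logarithmically (base of 10) transformed titers for serogroup A". Non-inferiority requires a lower 95% limit for the ratio above 0.5.

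The analyses of this ratio are:

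- the per-protocol ANCOVA, with a conditional repeat in the full analysis set (SAP 6.4.1);
- an ANOVA without the Day 1 titer, and a permutation test that reassigns vaccine but leaves the titers alone (SAP 6.4.2);
- subgroups by sex, race, country and baseline seronegativity (SAP 5.1.7).

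They change the analysis set, the covariate, the reference distribution or the subgroup. None changes the substituted value. SAP 6.4.1 also plans between-group differences, with 95% intervals, for the four-fold rise and for titers at or above 8 or the LLOQ. The table list sits elsewhere: "The TFL TOC provides the list of tables/listings and figures needed for the study report". That list is not among the documents.

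**The concern.** Replacing a left tail by one constant puts a floor under the data. If the liquid vaccine, aged to about 30% free serogroup A saccharide, gives lower titers, more of its values reach the floor, and part of the loss is hidden. The ratio then moves towards 1 and the SD shrinks. Both favour non-inferiority. The only analysis labelled as a sensitivity analysis keeps the titers as they are, so it cannot reveal this.

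The LOD had not been set when the protocol was written (Protocol 5.7.5), so the rule was chosen without a stated share of titers that it would affect. At stake is whether a lower limit just above 0.5, in a study meant to support release specifications (Protocol 1.2.1), could owe its position to the choice of LOD/2.

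**Working it through.** **Inputs.** Protocol 10.3: 437 evaluable per arm, log10 SD 0.929, planned ratio 0.8, margin 0.5, one-sided 0.025. The share of controls below the LOD at Day 29 is not given; 2% to 20% is assumed, and up to 30% for power.

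**1. The plan's own figure.** Distance from the margin: log10(0.8/0.5) = 0.2041. Standard error: 0.929 × √(2/437) = 0.0628. Power: Φ(0.2041/0.0628 − 1.96) = 90.1% (noncentral t: 90.0%). The stated figure of about 90% reproduces.

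**2. Shift without a distributional model.** Replacing LOD/2 by c × LOD multiplies the unadjusted GMT ratio by (c/0.5)^(pL − pC), where pL and pC are the Day 29 shares below the LOD in the liquid and control arms.

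| pL − pC | value doubled to LOD | value halved to LOD/4 |
|---|---|---|
| 0 | 1.000 | 1.000 |
| 2 points | 1.014 | 0.986 |
| 5 points | 1.035 | 0.966 |
| 10 points | 1.072 | 0.933 |

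At the planning SD the 95% half-width is 0.1234 on the log10 scale, so the smallest observed ratio that passes is 0.5 × 10^0.1234 = 0.664. The substituted value can change the conclusion for observed ratios close to that. An observed 0.8 has lower limit 0.8 × 10^−0.1234 = 0.602. With the width held fixed, halving the substituted value would bring this down to 0.5 only if the arms differed by log2(0.602/0.5) = 0.27, or 27 points.

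**3. Effect against an uncensored log-normal ratio of exactly 0.50.** For log10 titers N(μ, σ²) and log10 LOD = L, write a = (L − μ)/σ, p = Φ(a) and c = L − log10(2). The derived titers have mean pc + μ(1 − p) + σφ(a) and second moment pc² + (μ² + σ²)(1 − p) + σ(μ + L)φ(a). The chance of passing is Φ((difference − log10 0.5)/SE − 1.96).

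Worked case, 10% of controls below the LOD, σ = 0.929, L = 0:

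- Control μ = 0.929 × 1.2816 = 1.1906; liquid μ = 1.1906 − 0.3010 = 0.8896.
- Derived means 1.2044 and 0.9225; difference −0.2820; apparent ratio 0.522.
- Derived variances 0.8049 and 0.7473; SE = √(1.5522/437) = 0.0596.
- Chance of passing: Φ((0.3010 − 0.2820)/0.0596 − 1.96) = Φ(−1.64) = 5.0%.

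| Controls below LOD | 2% | 5% | 10% | 20% |
|---|---|---|---|---|
| Apparent ratio, SD 0.929 | 0.503 | 0.509 | 0.522 | 0.554 |
| Chance of passing, SD 0.929 | 2.7% | 3.4% | 5.0% | 12.3% |
| Chance of passing, SD 0.7 | 2.6% | 3.2% | 5.0% | 14% |
| Chance of passing, SD 0.5 | 2.0% | 2.2% | 3.7% | 14% |

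Both size and direction depend on the assumed SD and share.

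**4. Power at the design ratio.** With an uncensored ratio of 0.8, SD 0.929 and 2% to 30% of controls below the LOD, power lies between 88% and over 99% for LOD/4, LOD/2, LOD/√2 and LOD.

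**5. What the planned percentages would show.** At a true ratio of 0.5 and SD 0.929, 10% or 20% of controls below the LOD means 17% or 30% in the liquid arm. For 10% against 16.9%, the difference is 0.069 with SE √((0.1 × 0.9 + 0.169 × 0.831)/437) = 0.023. A 95% interval therefore excludes zero with probability Φ(0.069/0.023 − 1.96), about 85%; for 20% it is about 94%. With a cut-off at twice the LOD the figures are about 93% and 96%. These use a simple normal approximation. Where the planned cut-offs lie relative to the LOD is unknown.

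**The case for a change.** The best case for acting is that the dependence is real and inexpensive to check. If 20% of controls were below the LOD, the step 3 calculation at SD 0.929 gives a pass rate of 4.1% with LOD/4, 12.3% with LOD/2 and 32.6% with LOD. The planned percentages can hint at a problem but do not recompute the ratio. A left-censored normal (Tobit) ANCOVA would hold close to 2.5% under log-normality: 2.4% to 2.7% in simulation over 2% to 20% of controls below the LOD, with an assumed baseline correlation of 0.3. It could be added without new data, and specifying it before unblinding is better than afterwards.

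It stands that no described analysis varies the value, and that the percentages do not test the ratio. The proposed remedy is less secure. If undetectable titers come from non-responders equally common in both arms, and the population ratio is exactly 0.50, LOD/2 is nearly unbiased (mean estimates 0.496 to 0.500) and the Tobit model is the more biased of the two (0.479 to 0.496). In that setting, at a population ratio of 0.8, LOD/2 passes and Tobit fails in up to 11% of trials, a false warning. Under log-normality the same disagreement occurs in 6.2% of trials in the main simulation at 20% below the LOD, and in about 8% at most across simulations. A disagreement could not be attributed to one cause or the other, and normality below the LOD cannot be tested.

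**Conclusion.** The concern describes the plan correctly but shows no error in it. SAP 11.2 supplies what Protocol 10.5 asked it to supply, the rule is unambiguous and identical in both arms, and the hypotheses in SAP 7.1 refer to log10 titers without mentioning an uncensored titer. For the titers as derived, the test keeps its 2.5% level. The 5.0% and 12.3% figures are error rates for a different quantity. They rest on log-normality below the LOD, on 0.929 being the SD of the uncensored titers (it is itself an upper confidence limit), and on a share below the LOD that the documents do not give. At 2% of controls the excess over 2.5% is 0.2 points, at 5% it is 0.9 points, and at small SDs it becomes a deficit.

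An added analysis would change neither the primary result nor the success criterion. If the Day 29 share below the LOD turns out to be appreciable or to differ between arms, the analysts can tabulate it with the existing seropositivity definition and repeat the ANCOVA with other values, for example LOD/4 and LOD. That needs no assumption about the distribution below the LOD. Such a table may already be in the table list, which is not available here. This is an optional robustness check, and the plan can stand as written.
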